3.7 Sample Size

The primary outcome of interest is development of HA-AKI during admission at our centre. The incidence of Hospital-acquired AKI at our centre at March 2017 was 1.19% based on one ongoing study (A prospective, multicenter, observational study to determine the incidence and outcome of Acute Kidney Injury among hospitalised patients in Malaysia). The nine variables to be investigated for predictors of HA-AKI are age, gender, ICU

admission, race, nephrotoxin use, diabetes mellitus, hypertension, congestive heart failure and chronic obstructive pulmonary disease. With an estimation of 15 events per predictor, a minimum of 135 events would be needed, translating to a minimal of 11345 patients at our centre required for the study. The study population fits the minimum sample size requirement as 170283 adult admissions were recorded in total (22788 for Year 2002, 41731 for Year 2007, 46330 for Year 2012 and 59434 for Year 2017).

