Specific Objectives	
• To determine the incidence pattern of Hospital-acquired Acute Kidney Injury in Hospital Selayang• To study the determinants associated with development of Hospital-acquired Acute Kidney Injury in Hospital Selayang• To describe the survival outcomes of admissions with Hospital-acquired Acute Kidney Injury, admissions with Community-acquired Acute Kidney Injury and admissions without Acute Kidney Injury in Hospital Selayang
Study endpoints/outcomes	Completion of data collection at the end of the study duration
Sample Size	170000 (minimum 11345 required)
Study Duration	1 year

1. Background and Significance

Acute kidney injury (AKI) is a common problem globally which imposed heavy illness burden to the healthcare system, especially in developing countries. (1, 2) AKI can occur in the community (termed as Community-acquired AKI (CA-AKI)) or in the hospital setting (termed as Hospital-acquired AKI (HA-AKI)). Studies have associated HA-AKI as a preventable disorder, and linked HA-AKI with several immediate and long-term outcomes adversely, such as length of hospitalization, morbidity, and residual renal function. (1, 3, 4) Moreover, delayed recovery to baseline kidney function after AKI episode is found to be associated with higher risk of adverse events and mortality. (5) The impact of HA-AKI is significantly profound, especially among HA-AKI survivors who lost their residual renal function, and remain dialysis dependent. (6)

There was an increasing trend in HA-AKI incidence among hospitalized patients.(6-8) This could be attributed to increased exposure to potentially preventable risk factors during hospitalization. (6) However, studies pertaining to Asian countries are scarce, especially Malaysia. Preventative strategies against HA-AKI could be formulated based on understanding of risk factors which could be identified earlier upon hospital admission. (4)

The purpose of this study is to compare the incidence trend of HA-AKI in Selayang Hospital for the past 15 years, as well as to determine characteristics predictive of such cases. Understanding of clinical variables associated with HA-AKI could facilitate strategies and approaches to prevent, recognize HA-AKI early and mitigate the disease burden of HA-AKI in future.

2. Objective

2.1 *General Objective*

To investigate the incidence, characteristics and outcomes of Hospital-acquired Acute Kidney Injury in Hospital Selayang over 15 years

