2.2 *Specific Objectives:*

- To determine the incidence pattern of Hospital-acquired Acute Kidney Injury in Hospital Selayang
- To study the determinants associated with development of Hospital-acquired Acute Kidney Injury in Hospital Selayang

- To describe the survival outcome pattern of admissions with Hospital-acquired Acute Kidney Injury, admissions with Community-acquired Acute Kidney Injury and admissions without Acute Kidney Injury in Hospital Selayang

3. Methodology

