3.1 Study Type and Design

This is a retrospective cohort study involving 5-yearly trend from 2002 to 2017 for analysis. Laboratory serum creatinine (SCr) results of all patients admitted during study period will be retrieved from the hospital Laboratory Information System. A preliminary screening list will be generated by using STATA program from the SCr results. The nephrologist will then determine HA-AKI as per inclusion and exclusion criteria. Data collectors will collect all relevant data from these patients.

[figure not shown]

Figure 1. Flow chart of the study

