3.10 Statistical Analysis Plan

The analyses will be performed using IBM SPSS Statistics for Windows (Version 23.0. Armonk, NY: IBM Corp.). Descriptive statistics will be utilized for selected variables. The results will be presented as frequencies and percentage for Categorical Data. Numerical Data which is normally distributed will be presented as mean and standard deviation while median and interquartile range will be presented for Numerical Data which is not normally distributed.

Comparing Numerical Data which is normally distributed between two groups will be analysed using the Independent t-test while Mann-Whitney test will be used if not normally distributed. Multiple logistic regression will be used to study association between risk factors (Numerical Data/Categorical Data) and outcome (Categorical Data). The survival analyses and survival curves from the date of diagnosis until death will be performed using the Kaplan-Meier method, to estimate the index hospitalisation survival rate. All probability values will be two-sided and a level of significance of less than 0.05 (p-value < 0.05) will be considered as statistically significant.

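### The stated purpose is to compare HA-AKI incidence across four periods, but no cross-period comparison or period covariate is named, and ICU admission and nephrotoxin use need not precede AKI

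*Combined protocol and SAP*

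**What the plan says.** Section 1 gives the aim: "The purpose of this study is to compare the incidence trend of HA-AKI in Selayang Hospital for the past 15 years". Section 3.1 describes the design in the same terms: "This is a retrospective cohort study involving 5-yearly trend from 2002 to 2017 for analysis". Section 3.2 defines four one-year admission windows.

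Section 3.7 states: "The nine variables to be investigated for predictors of HA-AKI are age, gender, ICU" admission; the rest are race, nephrotoxin use and four comorbidities. Study period is not listed, and no timing is attached to ICU admission or nephrotoxin use. Section 3.3 defines HA-AKI as AKI arising more than 48 hours after admission.

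Section 3.10 offers three tools that bear on this point:

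- Description: "The results will be presented as frequencies and percentage for Categorical Data".
- Two-group tests for numerical data: "Comparing Numerical Data which is normally distributed between two groups will be analysed using the Independent t-test", with Mann-Whitney as the alternative.
- Regression, with no covariates listed: "Multiple logistic regression will be used to study association between risk factors (Numerical Data/Categorical Data) and outcome (Categorical Data").

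On data collection, Section 3.1 has a nephrologist determine HA-AKI and then says: "Data collectors will collect all relevant data from these patients".

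**The concern.** There are three linked gaps.

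**Trend.** HA-AKI is a yes/no outcome over four periods. The only group tests in Section 3.10 are for numerical data in two groups. Percentages will display four incidences and logistic regression could carry a period term, but neither a test nor a period term is specified. The comparison that gives the study its purpose would be chosen after the data are seen.

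**Period as a covariate.** Followed as listed, the model pools cohorts spanning 15 years. Section 1 itself reports rising HA-AKI incidence and suggests rising in-hospital exposure as a cause. If both move with time, pooled odds ratios are confounded by period.

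**Timing.** Section 1 wants risk factors that can be recognised early, on admission, so that prevention can be planned. ICU transfer after AKI does not serve that aim, yet it counts as a predictor under the list as written. The same gap applies to nephrotoxin use.

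**Working it through.** **Inputs from Section 3.7:** incidence 1.19%; 15 events per predictor; nine predictors; adult admissions 22,788, 41,731, 46,330 and 59,434 (total 170,283). From Section 3.10: two-sided 0.05. Every other input below is an assumption.

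**1. The plan's own figure.** 9 × 15 = 135 events; 135 / 0.0119 = 11,344.5, rounded up to 11,345. It reproduces.

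**2. Room for period.** Four levels add three parameters.

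| Race counted as | Parameters | Events (× 15) | Admissions (/ 0.0119) |
|---|---|---|---|
| one parameter, as in 3.7 | 12 | 180 | 15,127 |
| three levels (assumed) | 13 | 195 | 16,387 |
| four levels (assumed) | 14 | 210 | 17,648 |

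Expected events at 1.19% throughout: 271 + 497 + 551 + 707 = 2,026 after rounding. The 180 events are reached if 180 / 2,026 = 8.9% of these stay in the model sample (17.8% if incidence is half as high).

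**3. Precision and choice of test.** The 95% CI half-width is 1.96 × √(0.0119 × 0.9881 / n), which gives 0.14, 0.10, 0.10 and 0.09 percentage points by period. The table gives power for a Cochran-Armitage test (scores 0 to 3) and for a 3-df chi-square test with noncentrality Σn(p − p̄)² / [p̄(1 − p̄)]. Admissions are treated as independent.

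| Assumed incidence, first to last period | Linear trend | 3-df |
|---|---|---|
| linear, 0.90% to 1.19% | 98% | 94% |
| linear, 0.98% to 1.19% | 83% | 68% |
| linear, 1.04% to 1.19% | 54% | 37% |
| 1.19, 0.95, 0.95, 1.19% | 32% | 99% |

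A linear test is better for a steady rise but can miss a U-shape. The first objective in Section 2.2 is an incidence pattern, so the 3-df test should lead.

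**4. Denominator.** Only admissions lasting beyond 48 hours can have HA-AKI. Assume a constant risk among them of 1.19 / 0.50 = 2.38%, and a share staying beyond 48 hours that falls linearly from 60% to 50%. Incidence per admission then falls from 0.60 × 2.38 = 1.43% to 1.19%. The linear test declares a trend with 86% probability, although risk among those exposed to it is unchanged.

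**5. Pooling over period.** Assume a true OR of 1 and incidence rising linearly from 0.6% to 1.19%. Within each cohort exposure is independent of outcome; the four 2×2 tables are then summed.

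| Exposure prevalence, first to last period | Pooled OR |
|---|---|
| 20% to 30% | 1.04 |
| 10% to 40% | 1.12 |
| 30% to 20% | 0.96 |
| 40% to 10% | 0.87 |

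With no change in incidence, the pooled OR is 1.00.

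**6. ICU transfer after AKI.** Assume a true OR of 1, 3% early ICU admission, and 1% later ICU admission in non-cases. Then P(ICU | no AKI) = 0.03 + 0.97 × 0.01 = 0.0397 and P(ICU | AKI) = 0.03 + 0.97x, where x is the proportion of the remaining cases who enter ICU after AKI.

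| x | P(ICU given AKI) | OR |
|---|---|---|
| 1% | 0.0397 | 1.0 |
| 2% | 0.0494 | 1.3 |
| 5% | 0.0785 | 2.1 |
| 10% | 0.127 | 3.5 |
| 20% | 0.224 | 7.0 |

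The bias is upward whenever x exceeds the 1% in non-cases. The documents give none of these inputs.

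**7. Who the non-cases are.** Assume a true OR of 1, 3% early ICU admission, and 15% in admissions with AKI by 48 hours. If such admissions form 1%, 3% or 5% of the non-cases, ICU use in non-cases is 3.12%, 3.36% or 3.60%, and the OR becomes 0.96, 0.89 or 0.83. Early AKI therefore has to be removed from the non-cases.

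**The case against.** The formal objective and the first study outcome are descriptive, and period percentages with the half-widths above would inform a reader without any test. Comparing a trend does not strictly require a hypothesis test, and the logistic regression in Section 3.10 admits a period factor. This stands: on the trend alone, the gap is closer to missing detail than to a wrong analysis.

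The list in Section 3.7 serves to justify a sample size, and the confounding from pooling is small even under large assumed shifts. This also stands. However, it is the only covariate list, and period is known from the admission date, so leaving it out gains nothing.

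Section 1 shows an intent to use early risk factors. That weakens the timing reading, but an intent is not a data rule, and no section supplies one.

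A reader might infer more than the documents support:

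- **That the study cannot show a trend.** It can describe one.
- **That period is definitely excluded from the model.** The list is not said to be closed.
- **That the ICU odds ratio is inflated by a known amount, or that any odds ratio is reversed.** Every input to those calculations is assumed.
- **That the study is too small.** The 11,345 is arithmetically right and the recorded admissions far exceed any revised minimum.

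**Conclusion.** The concern holds as a gap in specification that should be closed before data are extracted. The comparison that motivates the study is not named, the only covariate list omits period, and two listed predictors may be recorded after the outcome they are meant to predict.

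The timing gap carries the most weight, because it can bias a reported odds ratio if the list is followed as written. Its size cannot be determined from the documents, and no estimate is available for nephrotoxin use. Period confounding is probably modest and could go in either direction; the range of 0.87 to 1.12 rests on an assumed doubling of incidence and assumed shifts in exposure. The power figures rest on assumed incidences before 2017 and on independent admissions.

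**What to change.** 1. **Model.** In Section 3.10, list the covariates as the nine variables plus study period (four levels). Report the period effect unadjusted and adjusted in the same sample, with the 3-df test across periods and a linear trend as a secondary summary. Period comes from the admission date and adds three parameters.
2. **Incidence.** Report crude incidence with 95% CI by period on two denominators: all adult admissions, and admissions still in hospital and free of AKI at 48 hours. The first needs only case counts and admission totals. The second also needs length of stay and early AKI status for each admission.
3. **Exposure timing.** Count ICU admission and nephrotoxin use only if they precede AKI, with the same exposure window for cases and non-cases. One simple choice is the first 48 hours, among admissions at risk at 48 hours. This is the costly item. ICU, nephrotoxin and AKI dates must be recorded from records back to 2001, and exposure after 48 hours goes unassessed. With that window, the adjusted period effect could not show whether later in-hospital exposure explains a trend, and the report should say so.
4. **Non-cases.** Confirm that covariates are collected for non-cases. The wording in Section 3.1 could mean HA-AKI cases only. Section 2.2 plans survival description for "admissions with Community-acquired Acute Kidney Injury and admissions without Acute Kidney Injury in Hospital Selayang", but that does not settle whether the nine covariates are collected for them. Figure 1 is not shown in the text available and may answer this. If covariates are collected for cases only, neither the listed nor the revised logistic model can be fitted; the crude comparison of incidence per all admissions still can.
5. **Section 3.7 (secondary).** Restate the minimum by parameters: about 15,127 admissions, or 16,387 to 17,648 if race has three or four levels. These are admissions to screen, so also report the events that remain in the model.

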3.3 Inclusion Criteria

- a) Age of 18 and above at time of hospital admission
- b) HA-AKI is defined by any patient who developed AKI (as per definition below) after 48 hours of hospital admission.
- c) Definition of AKI(9):

- i. An increase in serum creatinine of 0.3 mg/dl (26.5 μ mol/l) within 48 hours *OR*
- ii. An increase in serum creatinine to more or equal to 1.5 times baseline, which is known or presumed to have occurred within the prior 7 days

d) Definition for baseline creatinine(9):

- i. The baseline creatinine level is defined as the creatinine level at or within 7 days before the hospital admission, *OR*
 - ii. at the hospital admission *OR*
 - iii. the lowest creatinine (excluding the post dialysis creatinine if dialysis is initiated) during the index hospitalisation for those whose baseline creatinine were unknown.

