3.4 Exclusion Criteria

- End Stage Renal Failure and on Renal Replacement Therapy (HD, PD or Renal Transplant)

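### Baseline kidney function is missing from the nine candidate predictors, although creatinine is already retrieved and the chance of being labelled a case depends on its starting level

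*Combined protocol and SAP*

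**What the plan says.** Section 3.7 names the predictors in one sentence: "The nine variables to be investigated for predictors of HA-AKI are age, gender, ICU" and then "admission, race, nephrotoxin use, diabetes mellitus, hypertension, congestive heart failure and chronic obstructive pulmonary disease". No measure of pre-existing kidney function is among them. Section 3.10 plans multiple logistic regression of outcome on risk factors but names no covariates, so the list in 3.7 is the only one.

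Four other places bear on this:

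- Section 1 wants characteristics that predict HA-AKI and can be recognised at admission. Section 2.2 speaks of associated determinants.
- Section 3.1 retrieves the serum creatinine results of all patients admitted in the study periods.
- Section 3.3(d) begins: "The baseline creatinine level is defined as the creatinine level at or within 7 days before the hospital admission". It then allows the admission value and, where baseline is unknown, the lowest value during the stay.
- The only exclusion, in section 3.4, is "End Stage Renal Failure and on Renal Replacement Therapy (HD, PD or Renal Transplant"). Chronic kidney disease short of that stays in the cohort.

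The sample size follows from the count of predictors: "With an estimation of 15 events per predictor, a minimum of 135 events would be needed". No reason is given for leaving baseline kidney function out.

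**The concern.** A study meant to guide prevention from what is known at admission leaves out a candidate that the laboratory extract already supplies for many patients.

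The case definition adds a second reason. Criterion 3.3(c)(i) is a fixed absolute rise within 48 hours. A patient who starts at a high creatinine meets it with a much smaller proportional change than one who starts low. Any listed predictor that goes with a higher starting creatinine can therefore pick up part of this labelling effect, whether or not it changes the risk of true injury. Diabetes, hypertension, heart failure and age are the obvious candidates. Without the baseline term, a reader of the fitted model cannot tell how much of such a coefficient runs through kidney function on arrival.

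**Working it through.** **1. The plan's own figure.** Inputs from 3.7: nine predictors, 15 events per predictor, incidence 1.19%.

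- Events: 9 × 15 = 135.
- Admissions: 135 / 0.0119 = 11,344.5, rounded up to 11,345.

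This reproduces the stated minimum ("translating to a minimal of 11345 patients at our centre required for the study"). The yearly counts also add up: 22,788 + 41,731 + 46,330 + 59,434 = 170,283.

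**2. Cost of adding baseline kidney function.** Same rule, N = 15 × terms / 0.0119, rounded up.

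| Terms in model | Events | Admissions |
|---|---|---|
| 9 (plan) | 135 | 11,345 |
| 10 (one continuous term added) | 150 | 12,606 |
| 12 (three category terms added) | 180 | 15,127 |
| 13 (four category terms added) | 195 | 16,387 |

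One term adds 12,606 − 11,345 = 1,261 admissions.

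**3. What is available.** If 1.19% held in all four periods (an assumption, since the study sets out to measure the trend), 170,283 × 0.0119 ≈ 2,026 events, or about 203 per term with ten terms. At one tenth of that incidence, 170,283 × 0.00119 ≈ 203 events, still above 150. Put another way, 150 / 2,026 = 7.4%: the ten-term minimum would be met even if only that share of expected events had a usable baseline.

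**4. How case labelling depends on starting creatinine.** Criterion c(i) is a 26.5 µmol/l rise; c(ii) is a rise to at least 1.5 times baseline. The starting values are illustrative.

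- From 60 µmol/l: 26.5 / 60 = 44%.
- From 300 µmol/l: 26.5 / 300 = 9%.
- The two criteria ask for the same rise at 26.5 / 0.5 = 53 µmol/l. Above that level c(i) needs the smaller rise, and the gap widens as creatinine goes up.

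This is arithmetic on the definition and needs no outside data.

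**5. Illustrative size for one coefficient (assumed inputs, none in the documents).** Let reduced kidney function have prevalence p1 in diabetics and p0 in others, and multiply HA-AKI risk by RR. In a crude two-group comparison, the diabetes risk ratio without adjustment is its adjusted value times (1 + p1(RR − 1)) / (1 + p0(RR − 1)).

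- p1 = 0.20, p0 = 0.10, RR = 1.5: 1.10 / 1.05 = 1.05.
- p1 = 0.30, p0 = 0.10, RR = 3: 1.60 / 1.20 = 1.33.
- p1 = 0.40, p0 = 0.10, RR = 4: 2.20 / 1.30 = 1.69.

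The range of 1.05 to 1.69 shows only that the shift could be trivial or material. It is not an estimate for the planned model, which already contains age, hypertension and heart failure.

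**The case against.** The strongest reply is that the plan promises association and prediction, not causal effects. Reduced kidney function may also lie on the pathway from diabetes, age or hypertension to HA-AKI. Leaving it out then gives a total effect, which is legitimate, and adjusting for it gives a direct effect. This stands. It is a reason to report both models, not a reason to have only the unadjusted one, and for a predictive aim the missing candidate is still a loss.

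A reader might go further and infer that the four coefficients are confounded. The documents do not support that. They give no data linking baseline function to these conditions or to HA-AKI, so only potential confounding or mediation can be claimed. For the same reason, the multipliers in step 5 should not be read as spurious risk ratios to be expected.

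A reader might also infer that a baseline under 3.3(d) must exist for every case. It need not: c(i) can be met from two in-hospital values without reference to that baseline, and the third option in 3.3(d) exists because some baselines are unknown.

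Finally, an admission value already raised by community-acquired AKI would look like poor baseline function. That objection is sound, and it limits which admissions the adjusted model should use.

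**Conclusion.** The omission is real and worth correcting. Baseline kidney function is absent from 3.7 and 3.10, patients with reduced function remain in the cohort, and criterion c(i) ties case labelling to starting creatinine (44% of 60 µmol/l against 9% of 300). Coefficients for diabetes, hypertension, heart failure and age may partly carry that dependence; the direction of the pathway and the size are unknown from the documents.

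The stated 11,345 is correct for nine terms and is not in dispute. Sample size is no obstacle to a tenth: 12,606 admissions is 7.4% of 170,283. That comparison rests on the plan's 1.19% incidence and its 15-events rule, and it survives a tenfold lower incidence.

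**What to change.** 1. In 3.7 and 3.10, add baseline eGFR or creatinine as a tenth predictor. Take it from the pre-admission or admission value only. Never use the in-hospital nadir of 3.3(d)(iii) as a predictor, because it can postdate the event.
2. Report the logistic model with and without this term, and say that adjustment may move an estimate from a total towards a direct effect.
3. Fit the model in admissions without AKI at admission, so that community-acquired AKI is excluded and an acutely raised value is not read as poor baseline. Write down the rule used to identify these admissions; 3.3 gives none for community-acquired AKI.
4. If a missing-value indicator is used, report a complete-case analysis beside it. The indicator alone can leave bias, since testing probably depends on how ill the patient is.
5. Repeat the model with case status defined by c(ii) alone, stating in advance how patients who meet only c(i) are treated. Present this as a sensitivity analysis: c(ii) has its own link to baseline, since a value that is low by chance makes a 1.5-fold rise easier to reach.
6. Restate the minimum as 150 events and 12,606 admissions for one continuous term, or more if categories are used (15,127 for three added terms).

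The cost is one derived variable, an additional model and a sensitivity analysis, and restated figures, with no new data source. The downside is that admissions with no usable pre-event creatinine drop out of the adjusted model or need explicit handling.

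### The minimum is set in patients but met in admissions, and no rule covers repeat admissions, so p-values for patient-level predictors can be somewhat too small

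*Combined protocol and SAP*

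**What the plan says.** Section 3.7 defines the outcome at admission level: "The primary outcome of interest is development of HA-AKI during admission at our centre". It takes an incidence from another study ("The incidence of Hospital-acquired AKI at our centre at March 2017 was 1.19% based on one ongoing study") without saying whether the denominator was patients or admissions. From nine predictors it reasons "With an estimation of 15 events per predictor, a minimum of 135 events would be needed". Dividing that event count by the incidence gives its minimum, which it expresses in people: "translating to a minimal of 11345 patients at our centre required for the study". It then concludes: "The study population fits the minimum sample size requirement as 170283 adult admissions were recorded in total". The synopsis gives the sample size as 170000, with no unit.

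The unit also shifts elsewhere. Section 3.3 defines a case by patient. The survival objective in section 2.2 concerns admissions. Section 3.4 excludes only end-stage renal failure on renal replacement therapy, so a second or third admission of the same person stays in.

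On analysis, section 3.10 says "Multiple logistic regression will be used to study association between risk factors". It also plans Kaplan-Meier curves from diagnosis to death. It states no first-admission rule, clustered standard error, GEE or random effect. Tests are two-sided at 0.05.

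**The concern.** A person admitted several times brings the same gender, race and chronic conditions, and much the same kidney risk, to each admission. Ordinary logistic regression treats those records as independent. For a predictor that does not change within a person, this overstates the information in the data: the standard error is too small and the test rejects too often. Seven of the nine predictors are of that kind. The other two, ICU admission and nephrotoxin use, can differ from one admission to the next.

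The survival curves have a related problem. Every admission of a person except the last must have ended alive, so admission-level records are not independent there either.

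The incidence figure is affected too, whatever the correlation. Incidence per admission and per patient are different quantities, and the study's purpose is a trend over four periods in which recorded admissions rose from 22788 to 59434 (2.6-fold). If part of that rise is more admissions per person, the two trends can diverge with no change in risk per admission.

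**Working it through.** **1. The plan's own figure.** Inputs from section 3.7: 9 predictors, 15 events each, incidence 1.19%.

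- Events: 9 × 15 = 135.
- Minimum: 135 / 0.0119 = 11344.5, rounded up to 11345. The stated figure reproduces.
- Admissions: 22788 + 41731 + 46330 + 59434 = 170283. This also reproduces.

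**2. Does the change of unit undo the adequacy claim?** 170283 / 11345 = 15.0, and 170283 × 0.0119 ≈ 2026 expected events against 135. The number of unique patients would fall below 11345 only if patients averaged more than 15 admissions. Allowing for clustering, the design effect is DE = 1 + (m_w − 1) × ICC, where m_w is the size-weighted mean number of admissions per patient, (1 + CV²) × m. Over a deliberately wide grid (m = 1.2 to 3, CV 0 to 1, ICC 0.01 to 0.30), DE runs from 1.002 to 2.50. The largest requirement is 11345 × 2.50 ≈ 28363 admissions, still far below 170283.

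**3. What within-patient correlation is plausible at this event rate?** The documents give none, so it is assumed. For a binary event with risk p, the risk in another admission, given an event in one, is p + ICC × (1 − p). With p = 0.0119:

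- ICC 0.2: 0.0119 + 0.2 × 0.9881 = 0.2095, or 17.6 times the average risk.
- ICC 0.3: 0.0119 + 0.3 × 0.9881 = 0.3083, or 26 times.

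Both look too strong. A patient random intercept (log-odds scale) with SD 1 corresponds to an ICC of about 0.018, and SD 2 to about 0.12. SD 1 to 2 is taken as the working range.

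**4. Size of the effect for a patient-level predictor.** Simulation: 20000 patients, 300 runs per scenario, 1.19% event rate, a variable number of admissions per patient averaging 1.3 or 2.0, no true predictor effect. The naive standard error is compared with the patient-clustered one. The last column is DE from step 2, with m_w = 1.67 (mean 1.3) or 3.5 (mean 2.0) and the ICC from step 3.

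| Mean admissions | SD | Naive SE | Clustered SE | Ratio | Naive rejection at 5% | √DE by formula |
|---|---|---|---|---|---|---|
| 1.3 | 1 | 0.1253 | 0.1260 | 1.01 | 4.7% | 1.006 |
| 1.3 | 2 | 0.1253 | 0.1303 | 1.04 | 6.0% | 1.040 |
| 2.0 | 1 | 0.1007 | 0.1030 | 1.02 | 8.3% | 1.022 |
| 2.0 | 2 | 0.1006 | 0.1144 | 1.14 | 10.0% | 1.142 |

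Formula and simulation agree on the standard errors. The rejection rates are rougher: with 300 runs, a rate of 10% has a Monte Carlo standard error of √(0.1 × 0.9 / 300) = 1.7 percentage points. The formula 2[1 − Φ(1.96/ratio)] gives about 8.5% for the last row and 5.5% for the third, so about 10% is best read as an upper figure.

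**5. A predictor that varies independently between admissions.** In the strongest scenario, the naive standard error was 0.1157 and the clustered one 0.1158. There is no understatement.

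**6. Incidence by unit.** If 1.19% is per admission, then with 1.3 to 2.0 admissions per patient the per-patient figure could be as high as 1.19% × 1.3 = 1.55% to 1.19% × 2.0 = 2.38%. These are upper bounds, reached only if no patient has two events.

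**The case against.** The strongest reply is that the documents never say each admission is a regression row. Section 3.3 speaks of patients, section 3.1 of collecting data from patients, and sections 3.3 and 3.10 refer to an index hospitalisation, which could mean one stay per person. This stands as a limit: the understatement is conditional on the row unit. It does not remove the point. If one stay per person was meant, 170000 is not the sample size and the rule for choosing the stay is missing. Either way the plan needs a sentence it does not have.

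It is also fair to say that the effect is probably small. Three of the four scenarios give 4% or less, and the regression adjusts for chronic conditions that would be expected to explain part of the within-patient correlation. That stands, and it sets the size of the conclusion.

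A reader might infer three stronger things that the documents do not support:

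- That all standard errors are too small. The check in step 5 shows this need not hold for ICU admission or nephrotoxin use.
- That the study is too small because patients and admissions were confused. The 15-fold margin rules this out on the stated counts.
- That published confidence intervals will be too narrow. Section 3.10 specifies p-values and promises no intervals, so the direct consequence is for the tests.

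**Conclusion.** The concern holds in a limited form. The unit of analysis is not defined, the minimum and the cohort are counted in different units, and there is no method for repeat admissions. If admissions are the rows, which is the natural reading of sections 3.7 and 2.2 and the synopsis, tests of the seven predictors that are stable within a patient will tend to reject too often. The true standard error is about 1% to 14% larger than the naive one, probably by only a few percent in most cases, and the true error rate of a nominal 5% test is at most about 10%. These sizes rest on assumed values (1.3 to 2.0 admissions per patient, random-intercept SD 1 to 2, incidence 1.19%), because the documents give no count of unique patients and no correlation. The ambiguity in the incidence figure depends on neither the correlation nor the regression. The plan should be corrected, but neither its feasibility nor its sample size is in doubt.

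**What to change.** - In sections 3.7 and 3.10, name the admission as the unit of analysis and restate the minimum as 11345 admissions.
- Fit the logistic model with patient-clustered robust standard errors or GEE, with the patient as cluster across all four periods.
- Use the same unit in the numerator and denominator of incidence, and report unique patients and admissions per patient for each period.
- Add a sensitivity analysis limited to the first eligible admission per patient, for the regression and for the survival curves. It should not replace the main survival analysis, because deaths in later admissions drop out of it.

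The cost is small: slightly wider error bars and a few more lines in the plan. The one practical condition is the study number. Section 3.15 links names to a study identification number but does not say that one person keeps the same number across periods. It must do so for the clustering to work. No new clinical data are needed.
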